### 8.3 Partial or Missing Safety Information

A missing AE intensity is not imputed. AEs with missing intensity are included in the AE tables for All Grades. AEs with missing relationship are included in tables of “related” AEs.

### 8.4 Visit Week Windows

For longitudinal presentations, values are first selected within their respective study periods (see Section 6.1). Next, windows around scheduled measurement times are constructed based on the midpoint between scheduled measurement visits and the value closest to the scheduled visit for each measurement is selected from those that fall within the window.

Visit windows are defined in Table 8.4-1:

**Table 8.4-1: Visit Week Windows**

Week	On Treatment or ETV Treatment (Combined with or without Long-Term Follow-up)	Off-Treatment or Long-Term Follow-up	On Treatment/ETV treatment and Long-Term Follow-up Combined (Tanner Stage only)
0*	Day ≤ 1	Day ≤ Last dose + 5	Day ≤ 1
4	> 2 - 6 wks#	--	--
6	--	≤ 9 wks	--
8	> 6 - 10 wks#	--	--
12	> 10 - 18 wks	> 9 - 18 wks	--
24	> 18 - 30 wks	> 18 - 30 wks	> 12 - 36 wks
36	> 30 - 42 wks	> 30 - 42 wks	--
48	> 42 - 54 wks	> 42 - 54 wks	> 36 - 60 wks
60	> 54 - 66 wks	> 54 - 66 wks	--
72	> 66 - 78 wks	> 66 - 78 wks	> 60 - 84 wks
84	> 78 - 90 wks	> 78 - 90 wks	--
96	> 90 - 102 wks	> 90 - 102 wks	> 84 - 108 wks
108	> 102 - 114 wks	> 102 - 114 wks	--
120	> 114- 126 wks	> 114- 126 wks	> 108 - 132 wks
132	> 126 - 138 wks	> 126 - 138 wks	--
144	> 138 - 150 wks	> 138 - 150 wks	> 132 - 156 wks
156	> 150 - 162 wks	> 150 - 162 wks	--
168	> 162 - 174 wks	> 162 - 174 wks	> 156 - 180 wks
180	> 174 - 186 wks	> 174 - 186 wks	--

**Table 8.4-1: Visit Week Windows**

Week	On Treatment or ETV Treatment (Combined with or without Long-Term Follow-up)	Off-Treatment or Long-Term Follow-up	On Treatment/ETV treatment and Long-Term Follow-up Combined (Tanner Stage only)
192	> 186 - 198 wks	> 186 - 198 wks	> 180 - 204 wks
204	> 198 - 210 wks	> 198 - 210 wks	--
216	> 210 - 222 wks	> 210 - 222 wks	> 204 - 228 wks
228	> 222 - 234 wks	> 222 - 234 wks	
240	> 234 wks	> 234 wks	> 228 wks

\* “Week 0” is formatted according to treatment period: “Baseline” for the on-treatment period; “ETV Baseline” for the ETV treatment period; “EOD” for the off-treatment and long-term follow-up periods.

# On treatment (combined with or without long-term follow-up) only.

Additional visit windows after Week 240 are defined analogously as needed.

For the on-treatment period, weeks are calculated as (measurement date - first dose date of study therapy + 1)/7. This also applies to the on-treatment and long-term follow-up periods combined.

For the ETV treatment period, weeks are calculated as (measurement date - first dose date of active ETV + 1)/7. This also applies to the ETV treatment and long-term follow-up periods combined.

For the off-treatment and long-term follow-up periods, weeks are calculated as (measurement date - last dose date of study therapy)/7.

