4 INVESTIGATIONAL PLAN

4.1 Study Design and Duration

[figure not shown]
This is a comparative, randomized, double-blinded, placebo-control, multicenter study, assessing the efficacy and safety of oral ETV in pediatric subjects with chronic HBV infection who are HBeAg-positive and nucleos[t]ide naive (< 12 weeks of prior therapy with any nucleos[t]ide antiviral agent with activity against hepatitis B virus). Chronic HBV-infected children and adolescents from 2 to < 18 years of age will be enrolled. Approximately 180 subjects will be randomized 2:1 to ETV or placebo (PLB) for a maximum of 96 weeks of blinded therapy, with the analysis of the primary endpoint at Week 48 to be conducted for the first 123 treated subjects. The randomization will be stratified by age group (2 to ≤ 6 yrs; > 6 to ≤ 12 yrs; > 12 to < 18 yrs). To ensure adequate representation, the target enrollment will be 30 subjects for each age group, with a minimum requirement of 18 subjects. At Week 52 an assessment of HBeAg seroconversion shall be performed based on Week 48 serology results. At the Week 52 assessment, all subjects who achieve HBeAg seroconversion will remain on blinded therapy through Week 96; subjects without HBeAg seroconversion will be switched to open-label ETV. Thereafter, assessment of HBeAg seroconversion shall be conducted at study Weeks 100 and 148 during the open-label treatment. Study subjects who achieve HBeAg seroconversion during open-label ETV at the respective assessment time points shall receive up to an additional 48 weeks of study treatment for consolidation. Open-label ETV may therefore be continued up to Week 144 in ETV

randomized subjects and Week 192 for placebo randomized subjects. All randomized study subjects who do not achieve HBeAg seroconversion will receive a maximum of 96 weeks of study ETV therapy (Figure 4.1).

After completing the blinded treatment or the open-label phase, all subjects will be followed in an observational long-term follow up (LTFU) phase until they complete a total of 5 years of study participation from the start of blinded treatment.

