A subject who experiences an extreme elevation of ALT due to acute exacerbation of CHB is eligible to receive rescue open-label ETV from the study's sponsor at the request of their principal investigator and after discussion and approval by the BMS Central Medical Monitor, for up to 96 consecutive weeks, in an effort to optimize patient safety. Rescue open-label study ETV will be limited to those subjects who do not have access to acceptable alternative anti-HBV therapy. Upon completion of rescue open-label ETV, subjects will remain on study until they complete a total of 5 years of study participation from the start of blinded treatment or 48 weeks beyond the completion of rescue open-label ETV; whichever is later.

Figure 4.1: AI463189 Study Schema

The total duration of the study will be 264 weeks (5 years) or 48 weeks beyond the completion of rescue open-label ETV initiated for the purpose of treating an extreme elevation of ALT due to acute exacerbation of CHB; whichever is later; the end of the study is defined as the date of the last follow-up visit for the last subject treated. Study visits will occur at screening, Baseline, Weeks 4, 8, 12, and then every 12 weeks during study treatment. Additional ‘On Treatment’ visits to modify or discontinue study drug based on HBeAg assessments will occur at Weeks 52, 100, and 148, if needed. At selected sites, a subset of up to 9 treated subjects in each age cohort will have 4 plasma specimens collected for semi-intense pharmacokinetic assessments during a single visit between study Day 14 and Week 4. Once in the observational LTFU phase, study visits will occur at Weeks 6, 12, and then every 12 weeks until completion of a total of 264 weeks of ‘on-study follow-up’ or 48 weeks beyond the completion of rescue open-label ETV initiated for the purpose of treating an extreme elevation of ALT due to acute exacerbation of CHB; whichever is later.

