6 STUDY ASSESSMENTS AND PROCEDURES

6.1 Flow Chart/Time and Events Schedule

Table 6.1: Flow Chart for Protocol AI463189

Procedure	Screening ≤ 6 Weeks prior to Randomization	Randomize Initiate study drug (Day 1) within 72 hours	On Study Treatment Weeks 4, 8, 12 ± 3 days, and every 12 weeks ± 5 days up to end of study drug dosing	Weeks 52, 100 and 148 ± 10 days (if needed) ^a	End of Treatment (Scheduled or Early)	Observational LTFU ^b Weeks 6, 12, and every 12 weeks ± 5 days Up to 264 weeks total study participation [or 48 weeks beyond completion of rescue open- label ETV used for treatment of an extreme elevation of ALT due to acute exacerbation of CHB; whichever is later]	Protocol Section
Eligibility Assessments							
Informed Consent	X						3.3
Inclusion/Exclusion Criteria	X						4.2
Medical & anti HBV history ^c	X						4.2
HCV, HDV serology (1 mL)	X						6.9
Alpha Fetoprotein (1 mL)	X						6.9

Table 6.1: Flow Chart for Protocol AI463189

Procedure	Screening ≤ 6 Weeks prior to Randomization	Randomize Initiate study drug (Day 1) within 72 hours	On Study Treatment Weeks 4, 8, 12 ± 3 days, and every 12 weeks ± 5 days up to end of study drug dosing	Weeks 52, 100 and 148 ± 10 days (if needed) ^a	End of Treatment (Scheduled or Early)	Observational LTFU ^b Weeks 6, 12, and every 12 weeks ± 5 days Up to 264 weeks total study participation [or 48 weeks beyond completion of rescue open- label ETV used for treatment of an extreme elevation of ALT due to acute exacerbation of CHB; whichever is later]	Protocol Section
Safety Assessments							
Physical Examination	X				X		6.3
Targeted Physical Examination (including neurologic assessment)		X	X			X ^d	6.3
Vital Signs including height, and weight	X	X	X		X	X	6.3
Tanner Stage Assessment		X	Week 24 and every 24 weeks		X	Week 24 and every 24 weeks	App 3
Pretreatment Events Assessment		X					6.3
Adverse Events Assessment			X		X	X ^e	6.3

Table 6.1: Flow Chart for Protocol AI463189

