### **7.5.7 All ETV On-Treatment Efficacy**

The following binary endpoints are summarized with response rates using NC = M at baseline and each scheduled visit on ETV treatment through Week 144 for the All ETV Efficacy Cohort (see [Sections 6.3](#) and [8.4](#)):

- HBV DNA < 50 IU/mL
- HBV DNA < 50 IU/mL and HBeAg seroconversion
- HBV DNA < 50 IU/mL and ALT normalization
- HBV DNA < LOQ
- HBV DNA < LLD
- HBV DNA < LOQ, LOQ - < 50, 50 - < 172, 172 - < 1,720, 1,720 - < 17,200 and  $\geq 17,200$  IU/mL
- ALT normalization
- HBeAg loss
- HBeAg seroconversion
- HBsAg loss
- HBsAg seroconversion

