## 8.9 Derived Dates

Derived dates that are used commonly in analyses are defined as follows. Derivations of dose dates exclude rescue open-label ETV.

- First dose date of study therapy is the earliest start date of drug (ie, blinded therapy [ETV active or PBO] or open-label ETV) identified from valid dosing records, ie, non-missing start date and number of units per day > 0, from blinded therapy study medication CRFs. This date is used to identify treated subjects and to distinguish measurements across study periods. Note that this is also first dose date of blinded study therapy.

- Dose end date of study therapy is the latest start or end dates of drug (ie, blinded therapy [ETV active or PBO] or open-label ETV) identified from valid dosing records, ie, non-missing start or end date and number of units per day > 0 or total dose > 0. This date is used to assess time on study therapy.
- Last dose date of study therapy is the dose end date of study therapy derived only for subjects with an end of treatment subject status CRF indicating whether the subject completed the treatment period. This date is used to exclude data in antiviral activity and safety analyses, and to distinguish measurements across study periods.
- Dose end date of blinded therapy is the latest start or end date of blinded therapy (ETV active or PBO) identified from valid dosing records, ie, non-missing start or end date and number of units per day > 0, from blinded therapy study medication CRFs. This date is used to assess time on blinded study therapy.
- First dose date of open-label ETV is the earliest start date of open-label ETV identified from valid dosing records, ie, non-missing start date and total dose > 0, from open-label study medication CRFs. This date is used to distinguish measurements across blinded vs open-label treatment, and to assess time on open-label therapy.
- Dose end date of open-label ETV is the latest start or end date of open-label ETV identified from valid dosing records, ie, non-missing start or end date and total dose > 0, from open-label study medication CRFs. This date is used to assess time on open-label therapy.
- First dose date of active ETV is the first dose date of study therapy for ETV-randomized subjects, and the first dose date of open-label ETV for PBO-randomized subjects. This date is used to identify all ETV-treated subjects and to distinguish measurements across study periods.

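### On the ETV-treatment clock, Table 8.4-1 has no window between Day 2 and week 10, so almost no switched placebo child contributes to the All ETV Week 12 summaries

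*SAP*

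**What the plan says.** SAP 8.4 states a general rule: "windows around scheduled measurement times are constructed based on the midpoint between scheduled measurement visits", with the value closest to the scheduled visit chosen inside each window. Table 8.4-1 then prints the bounds. Its first column serves both the on-treatment period and the ETV-treatment period. Week 4 (> 2 - 6 weeks) and Week 8 (> 6 - 10 weeks) carry the # mark, which restricts them to "On treatment (combined with or without long-term follow-up) only". Week 12 (> 10 - 18 weeks) carries no mark and so applies to both clocks.

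On the ETV clock, "weeks are calculated as (measurement date - first dose date of active ETV + 1)/7". SAP 8.9 starts that clock at "the first dose date of open-label ETV for PBO-randomized subjects". Protocol 4.1 says that, at the Week 52 assessment, "subjects without HBeAg seroconversion will be switched to open-label ETV". It does not restart the visit calendar at the switch: "Study visits will occur at screening, Baseline, Weeks 4, 8, 12, and then every 12 weeks during study treatment".

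The ETV clock is used in SAP 7.5.7 ("each scheduled visit on ETV treatment through Week 144 for the All ETV Efficacy Cohort"), in the All ETV part of laboratory tests over time (7.6.6.2) and in the All ETV part of growth (7.6.7).

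**The concern.** The Week 12 lower bound of 10 weeks is the midpoint of Weeks 8 and 12. Once Week 8 is removed from the ETV clock, that bound has no basis, and a gap opens between the ETV baseline window (Day ≤ 1) and week 10.0. The first scheduled measurement of a switched placebo child after starting ETV falls in that gap.

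What is at stake is how adjacent columns of the All ETV tables are read. SAP 7.5.7 uses non-completer = missing, so each denominator is the set of children with data in that window. If switchers are absent at Week 12 and present at Week 24, a change between those columns mixes time on ETV with a change in who is counted. The table has no note to say so.

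**Working it through.** **1. Reproduce the printed bounds.** On-treatment visits at 0, 4, 8, 12 and 24 weeks have midpoints 2, 6, 10 and 18. These give > 2 - 6, > 6 - 10 and > 10 - 18, exactly as printed. The other columns follow their own visits in the same way: off-treatment Week 12 starts at > 9 (midpoint of 6 and 12), and Tanner Week 24 starts at > 12 (midpoint of 0 and 24).

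**2. Apply the same rule to the ETV clock.** With Weeks 4 and 8 removed, the visits are 0, 12 and 24, with midpoints 6 and 18. Week 12 would be > 6 - 18 weeks, not > 10 - 18.

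**3. Place the switchers' visits.** Inputs: first open-label dose at Week 52 ± 10 days, and 12-weekly visits ± 5 days (Protocol Table 6.1). ETV week = (visit day − first ETV dose day + 1)/7. At nominal dates:

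| Study week | ETV week | Window as printed |
|---|---|---|
| 60 | (56 + 1)/7 = 8.1 | none |
| 72 | (140 + 1)/7 = 20.1 | Week 24 |
| 84 | (224 + 1)/7 = 32.1 | Week 36 |
| 96 | (308 + 1)/7 = 44.1 | Week 48 |

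**4. Allow for the tolerances.** The interval can move by 10 + 5 = 15 days either way.
- Week 60: (56 − 15 + 1)/7 = 6.0 to (56 + 15 + 1)/7 = 10.3.
- Week 72: (140 − 15 + 1)/7 = 18.0 to (140 + 15 + 1)/7 = 22.3.

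There are 21 × 11 = 231 combinations of switch day and visit day. Week 60 has no window in 228 of them (98.7%) and falls in Week 12 in 3. Week 72 falls in Week 24 in 230 and in Week 12 in 1. Taking both visits together (21 × 11 × 11 = 2,541 combinations), a child has a value in ETV Week 12 in 44, or 1.7%. These percentages give every permitted day equal weight, which is an assumption; the ranges do not depend on it.

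**5. Count the children.** The protocol plans 120 ETV and 60 placebo children, with 10% dropout per year and 10% placebo seroconversion (Synopsis and 8.1). Switchers: 60 × 0.9 × 0.9 = 48.6, about 49. Share of the All ETV cohort: 48.6/(120 + 48.6) = 28.8%.

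**6. Effect on a by-visit rate.** Let w = 0.29 be the switchers' share, ignoring differential missingness. The change from Week 12 to Week 24 is then approximately the change in the ETV-randomised children plus w × (the switchers' rate in the Week 24 window − the ETV-randomised rate at Week 24). The second term is purely a change of composition.

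**7. Check the remedy.** With Week 12 at > 6 - 18, the Week 60 visit falls in Week 12 in 230 of 231 combinations. The exception is exactly 6.0 weeks.

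**The case against.** A reader might infer that the first on-ETV data of the switched children are lost from the report. The documents do not support that. The same visits are tabulated on the study clock:
- SAP 7.5.4 covers efficacy through Week 96 for placebo children who had not seroconverted at Week 48. Its remark that placebo is summarised only through Week 48 is best read as meaning the pooled placebo group.
- SAP 7.6.6.2 covers laboratory values through Week 96 for the Year 2 Safety Cohort, which has a separate group for placebo children on open-label ETV.
- SAP 7.6.7 covers growth for treated subjects and for the Year 2 Safety Cohort.

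A reader might also infer that every ETV-clock table is affected. Two items are not: INR is sampled only every 24 weeks, so Week 60 has no scheduled value, and Tanner stage has its own windows. Adverse events, worst-grade laboratory abnormalities and ALT flares on ETV do not use these windows.

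Nor does Week 12 contain ETV-randomised children exclusively. Besides the tolerance-edge cases, a placebo child who seroconverts by Week 48 and then reverts starts ETV at another time (Protocol 4.1.1); on the planning rates at most 60 × 0.9 × 0.1 = 5.4 children could do so. Unscheduled samples can also fall there.

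Three further points deserve weight. SAP 7.1 lets specified windows override the midpoint rule, and Table 8.4-1 does specify them. The affected efficacy rates carry no test or between-arm contrast, and reported denominators would reveal the change in numbers. The remedy places values from about ETV week 8 under a Week 12 label for one group.

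These points limit the severity. They do not explain the bound: the table gives no reason for keeping 10 weeks after removing Week 8, and the other columns were derived from their own visits. The early timing is already accepted at Weeks 24, 36 and 48, where switchers are seen at about weeks 20, 32 and 44, although four weeks is proportionally more at Week 12.

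**Conclusion.** The point holds as a minor defect in descriptive by-visit summaries. On the ETV clock, Day 2 through week 10.0 has no window, and the midpoint rule would have begun Week 12 at > 6 weeks. As a result, the Week 12 column for All ETV efficacy (7.5.7), laboratory values other than INR (7.6.6.2) and growth other than Tanner stage (7.6.7) is almost entirely the ETV-randomised arm. About 49 switchers, 29% of the cohort, join at Week 24.

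The size rests on the protocol's planning rates, on full enrolment of 180 and on switching within the Week 52 tolerance. The near-total absence of switchers from Week 12 follows from the calendar and needs no assumption beyond adherence to the visit windows. No primary or key secondary comparison is touched, and the ETV Week 48 column is sound: study Week 96 is at about ETV week 44, inside > 42 - 54 weeks.

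**What to change.** In Table 8.4-1, for the ETV-treatment period only, set Week 12 to > 6 - 18 weeks and keep the closest-to-scheduled-visit rule. The on-treatment bound stays at > 10 - 18 weeks. Because the column is shared, this needs a mark on the Week 12 cell.

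Add a footnote to the All ETV tables that values from children who switched at Week 52 are taken about 4 weeks before the nominal week: about ETV week 8 for Week 12, 20 for Week 24, 32 for Week 36 and 44 for Week 48.

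The cost is one table cell and one footnote, with no new data. ETV-randomised children keep their Week 12 value. Where it is missing, a Week 8 chemistry or growth value could stand in, which the footnote can also state. Extending the Week 4 and Week 8 windows to the ETV clock would lose no Week 60 visit either (Week 8 in 227 of 231 combinations, Week 12 in 3, Week 4 in 1), but switchers would still be missing from Week 12.

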### 8.5 Baseline and EOD Measurements

Baseline values are the last non-missing assessments taken prior and up to the first dose of study therapy, or the enrollment date for subject never receiving study therapy, unless specified otherwise.

HBV genotype is derived as the first non-missing assessment regardless of study period. Missing values include those that are labeled “ND” or “UAS”. Indeterminate values are not considered missing.

End of dosing (EOD) values are the last non-missing assessments taken after the first dose of study therapy and up to the last dose of study therapy plus 5 days.

For analyses of ETV treatment for the All ETV Efficacy and Safety Cohorts, the baseline values are the last non-missing assessments taken prior and up to the first dose of active ETV (i.e., “ETV baseline”). For these cohorts, the following parameters are derived only at baseline and

not re-derived at ETV baseline: gender, race, ethnicity, geographic region, country, HBV genotype.

Subjects are excluded from any changes from baseline (or EOD) analysis for which they have a missing baseline (or EOD) value.

## 8.6 HBV DNA Below LOQ or LLD

HBV DNA < LOQ is identified by the specify field “DETECTED BUT BELOW LOQ” or NOT DETECTED”.

HBV DNA < LLD is identified by the specify field “NOT DETECTED”.

In analyses of HBV DNA as a continuous variable, HBV DNA < LOQ or LLD is assigned a value 1 IU less than the LOQ i.e., 28 IU/mL.

## 8.7 Multiple Measurements

If more than one specific test result is reported in a given visit window, the result closest to the scheduled visit week is used in the analysis (as determined by the absolute difference in days between the planned visit and the measurement date). In addition:

- For HBV DNA by PCR from multiple HBV DNA samples collected on the same date, the one assayed at an earlier date is reported in the analysis.
- For multiple ALT, HBeAg and HBeAb values obtained from the same collection date, the ‘worst case’ is selected in the efficacy analyses (i.e., “POSITIVE” for HBeAg and “NEGATIVE” for HBeAb for subjects who were HBeAg-positive at baseline, and the highest ALT value after start of dosing).
- For growth parameters based on height and weight, the ‘worst case’ is selected in the safety analyses: if values are of equal distance or there are multiple values on same date, then select the pair (height, weight) with smallest percentile across all measurements.

## 8.8 Indeterminate Serology Results

Serum HBeAg, HBeAb, HBsAg and HBsAb values of “INDETERMINAT”, “BORDERLINE” and “EQUIVOCAL” are considered indeterminate.

For efficacy analyses in [Section 7.5](#), indeterminate values are imputed to be “worst case”, i.e., “POSITIVE” for HBeAg and “NEGATIVE” for HBeAb.

## 8.9 Derived Dates

Derived dates that are used commonly in analyses are defined as follows. Derivations of dose dates exclude rescue open-label ETV.

- First dose date of study therapy is the earliest start date of drug (ie, blinded therapy [ETV active or PBO] or open-label ETV) identified from valid dosing records, ie, non-missing start date and number of units per day > 0, from blinded therapy study medication CRFs. This date is used to identify treated subjects and to distinguish measurements across study periods. Note that this is also first dose date of blinded study therapy.

- Dose end date of study therapy is the latest start or end dates of drug (ie, blinded therapy [ETV active or PBO] or open-label ETV) identified from valid dosing records, ie, non-missing start or end date and number of units per day > 0 or total dose > 0. This date is used to assess time on study therapy.
- Last dose date of study therapy is the dose end date of study therapy derived only for subjects with an end of treatment subject status CRF indicating whether the subject completed the treatment period. This date is used to exclude data in antiviral activity and safety analyses, and to distinguish measurements across study periods.
- Dose end date of blinded therapy is the latest start or end date of blinded therapy (ETV active or PBO) identified from valid dosing records, ie, non-missing start or end date and number of units per day > 0, from blinded therapy study medication CRFs. This date is used to assess time on blinded study therapy.
- First dose date of open-label ETV is the earliest start date of open-label ETV identified from valid dosing records, ie, non-missing start date and total dose > 0, from open-label study medication CRFs. This date is used to distinguish measurements across blinded vs open-label treatment, and to assess time on open-label therapy.
- Dose end date of open-label ETV is the latest start or end date of open-label ETV identified from valid dosing records, ie, non-missing start or end date and total dose > 0, from open-label study medication CRFs. This date is used to assess time on open-label therapy.
- First dose date of active ETV is the first dose date of study therapy for ETV-randomized subjects, and the first dose date of open-label ETV for PBO-randomized subjects. This date is used to identify all ETV-treated subjects and to distinguish measurements across study periods.
- Dose end date of active ETV is the dose end date of study therapy for ETV-randomized subjects and the dose end date of open-label ETV for PBO-randomized subjects. This date is used to assess time on active ETV.
- Last dose date of active ETV is the dose end date of active ETV derived only when the last dose date of study therapy is not missing.
- Start date of rescue open-label ETV is the earliest start date of rescue open-label ETV identified from valid dosing records, ie, non-missing start date and total dose > 0, from rescue open-label ETV study medication CRFs.
- Start date of alternative ETV therapy is the earliest start date of (1) rescue open-label ETV, or (2) concomitant ETV taken on treatment or during long-term follow-up.
- Start date of alternative anti-HBV therapy is the earliest start date of (1) rescue open-label ETV, or (2) concomitant anti-HBV medication taken on treatment or during long-term follow-up.
- Last contact date is the death date, if it exists, or the latest of the following dates: randomization; first or last dose of study therapy; adverse event onset or resolution; hepatitis B related diagnosis; laboratory test (safety, pregnancy, serology and virology); liver biopsy; physical measurement; physical exam; neurologic exam; vital sign; non-study medication start or stop; last contact from end of treatment or end of study subject status; Tanner staging.

